## 11.0 Serious Adverse Event Reporting (SAE) for MD Anderson-Sponsored IND Protocols

An adverse event or suspected adverse reaction is considered "serious" if, in the view of either the investigator or the sponsor, it results in any of the following outcomes:

- Death
- A life-threatening adverse drug experience any adverse experience that places the
  patient, in the view of the initial reporter, at immediate risk of death from the adverse
  experience as it occurred. It does not include an adverse experience that, had it occurred
  in a more severe form, might have caused death.
- Inpatient hospitalization or prolongation of existing hospitalization
- A persistent or significant incapacity or substantial disruption of the ability to conduct normal life functions.
- A congenital anomaly/birth defect.

Important medical events that may not result in death, be life-threatening, or require hospitalization may be considered a serious adverse drug experience when, based upon appropriate medical judgment, they may jeopardize the patient or subject and may require medical or surgical intervention to prevent one of the outcomes listed in this definition. Examples of such medical events include allergic bronchospasm requiring intensive treatment in an emergency room or at home, blood dyscrasias or convulsions that do not result in inpatient hospitalization, or the development of drug dependency or drug abuse (21 CFR 312.32).

Important medical events as defined above, may also be considered serious adverse events. Any important medical event can and should be reported as an SAE if deemed appropriate by the Principal Investigator or the IND Sponsor, IND Office.

All events occurring during the conduct of a protocol and meeting the definition of a SAE must be reported to the IRB in accordance with the timeframes and procedures outlined in "The University of Texas M. D. Anderson Cancer Center Institutional Review Board Policy for Investigators on Reporting Unanticipated Adverse Events for Drugs and Devices". Unless stated otherwise in the protocol, all SAEs, expected or unexpected, must be reported to the IND Office, regardless of attribution (within 5 working days of knowledge of the event).

All life-threatening or fatal events, that are unexpected, and related to the study drug, must have a written report submitted within 24 hours (next working day) of knowledge of the event to the Safety Project Manager in the IND Office.

Unless otherwise noted, the electronic SAE application (eSAE) will be utilized for safety reporting to the IND Office and MDACC IRB. Serious adverse events will be captured from the time of the first protocol-specific intervention, until 30 days after the last dose of drug, unless the participant withdraws consent. Serious adverse events must be followed until clinical recovery is complete and laboratory tests have returned to baseline, progression of the event has stabilized, or there has been acceptable resolution of the event.

Additionally, any serious adverse events that occur after the 30 day time period that are related to the study treatment must be reported to the IND Office. This may include the development of a secondary malignancy.

All adverse events encountered during the study will be evaluated according to the NCI Common Toxicity Criteria (CTCAE) version 4.03.

The investigator or physician designee is responsible for verifying and providing source documentation for all adverse events and assigning attribution of all events for subjects enrolled.

## Reporting to FDA:

Serious adverse events will be forwarded to FDA by the IND Sponsor (Safety Project Manager IND Office) according to 21 CFR 312.32.

It is the responsibility of the PI and the research team to ensure serious adverse events are reported according to the Code of Federal Regulations, Good Clinical Practices, the protocol guidelines, the sponsor's guidelines, and Institutional Review Board policy.

# 12.0 Unanticipated Adverse Device Effect (UADE) Reporting for M. D. Anderson-Sponsored IDE Protocols

## **Unanticipated Adverse Device Effect**

Any serious adverse effect on health or safety or any life-threatening problem or death caused by, or associated with, a device, if that effect, problem, or death was not previously identified in nature, severity, or degree of incidence in the investigational plan or application (including a supplementary plan or application), or any other unanticipated serious problem associated with a device that relates to the rights, safety, or welfare of subjects" (21 CFR 812.3(s)).

Events that are related to the surgery will not be reported or recorded in the case report form.

All UADE will be reported to the IRB in accordance with the timeframes and procedures outlined in "The University of Texas M. D. Anderson Cancer Center Institutional Review Board Policy for Investigators on Reporting Unanticipated Adverse Events for Drugs and Devices".

Unless otherwise noted, the electronic SAE application (eSAE) will be utilized for safety reporting to the IND Office and IRB. Unanticipated Adverse Device Effects will be forwarded to FDA by the IND Sponsor (Safety Project Manager IND Office) according to 21 CFR 812.150.

It is the responsibility of the PI and the research team to ensure unanticipated adverse device effects are reported according to the Code of Federal Regulations, Good Clinical Practices, the protocol guidelines, the sponsor's guidelines, and Institutional Review Board policy.

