The additional exposure to light which will occur during imaging can also be compared to that received by newborn babies undergoing phototherapy for jaundice. The high-resolution fiber-optic microendoscope proposed for use here delivers 0.5 mW of 455 nm light to the tissue through a 0.8 mm diameter fiber-optic bundle, corresponding to an irradiance level of 100 mW/cm². The American Academy of Pediatrics defines intensive phototherapy as a spectral irradiance of at least 30 mW/cm² per nanometer over the 430-490 nm spectral band, equivalent to a total irradiance of 1.8 mW/cm² (24). Although the irradiance level is over 50-times higher with the fiber microendoscope system, a typical imaging session of 30 minutes (including imaging for routine care) is approximately 50-times shorter than a typical 24 hour (1440 minutes) phototherapy incubation, leading to an equivalent light dose in each scenario.

The imaging procedure will add approximately 10 minutes to the patient's time in the operating room. There is the rare possibility that there may be additional risks from the added time of additional sedation.

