The investigators and all employees and co-workers involved with this study shall not disclose or use for any purpose, other than performance of the study, any data, records or other unpublished, confidential information disclosed to those individuals for the purpose of the study. No patient identifiers will be used when analyzing the data or reporting the results.

For this protocol we will only capture adverse events that are determined by the PI to be definitely related to the proflavine and/or HRME imaging. Adverse events and serious adverse events related to the standard of care CKC will not be captured as part of the protocol data

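### The exclusions of cone- and surgery-related events in Sections 9.0 and 12.0 give no rule for shared causes and conflict with SAE reporting in Section 11.0

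*Combined protocol and SAP*

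**What the plan says.** **The research risk.** Section 7.0 says of the extra time: "The imaging procedure will add approximately 10 minutes to the patient's time in the operating room". It adds: "There is the rare possibility that there may be additional risks from the added time of additional sedation".

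**What is captured.** The last paragraph of Section 9.0 says the study will "only capture adverse events that are determined by the PI to be definitely related to the proflavine and/or HRME imaging".

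**What is excluded.** The same paragraph continues: "Adverse events and serious adverse events related to the standard of care CKC will not be captured as part of the protocol data". Section 12.0, directly after the UADE definition, says: "Events that are related to the surgery will not be reported or recorded in the case report form".

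**What Section 11.0 requires for serious events.**
- On the IRB: "All events occurring during the conduct of a protocol and meeting the definition of a SAE must be reported to the IRB".
- On the IND Office: "Unless stated otherwise in the protocol, all SAEs, expected or unexpected, must be reported to the IND Office, regardless of attribution".
- On the window: "Serious adverse events will be captured from the time of the first protocol-specific intervention, until 30 days after the last dose of drug".

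Section 11.0 also has all adverse events evaluated under CTCAE 4.03 and makes the investigator responsible for assigning attribution to every event.

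**What the data are for.** Section 10.0 evaluates safety in the first 5 patients and again after each further cohort of 5, to a total of 20.

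**The concern.** Under Section 6.0, the cervix is stained with proflavine and touched with the probe before the sterile prep. The same tissue is then coned in the same operating-room session. Section 7.0 lists bleeding and infection among the risks of the standard cone. If either follows in a study patient, a surgical explanation is always at hand, and an imaging contribution often cannot be ruled out. Shared attribution is therefore a foreseeable case in this design.

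Both exclusions apply to an event that is related to the cone or surgery. Neither says *solely* related. Read literally, a partly surgical event is excluded even if imaging may have contributed. At stake is whether the cohort safety evaluations can see the events that would bear on the imaging. For serious events, two sections also give the site opposite instructions.

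**Working it through.** The plan states no figure on this point, so the check is a reading of the rules side by side. Section 9.0 sets two conditions for an adverse event to enter the protocol data: (a) it is judged *definitely* related to proflavine and/or HRME imaging; (b) it is not related to the standard-of-care cone. Section 12.0 repeats (b) in wider terms: surgery rather than the cone, and neither reported nor recorded.

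| Event | Sections 9.0 and 12.0 | Sections 11.0 and 12.0 (SAE, UADE) | Result |
|---|---|---|---|
| Non-serious, due only to the cone | Excluded | SAE and UADE duties do not apply | Consistent, and a defensible choice |
| Non-serious, definitely due to imaging, not to the cone | Captured | SAE and UADE duties do not apply | Consistent |
| Non-serious, related to the cone and possibly to imaging | Fails (a) and fails (b) | Attribution is assigned, but no recording duty is stated | Can be left out |
| Non-serious, related to the cone and definitely to imaging | Passes (a), fails (b) | As above | Section 9.0 conflicts with itself; no precedence is given |
| Non-serious sedation event in the prolonged anaesthetic | Depends on whether HRME imaging includes the added time, and whether surgery includes its anaesthetic | As above | Undefined |
| Serious, related to the cone and possibly to imaging | Out of the protocol data; not reported | Captured; reported to the IRB; to the IND Office unless the protocol states otherwise | Contradiction |
| Serious, unanticipated, associated with the device and also with surgery | Not reported | Reportable as a UADE | Contradiction within Section 12.0 |

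Three points follow.

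1. **Relaxing condition (a) alone would not settle it.** If *definitely* became *possibly*, the third row would move to the fourth. The event would then meet both the capture rule and the exclusion, and no text says which prevails.
2. **The opening clause of the IND Office sentence is the weak link for serious events.** Sections 9.0 and 12.0 can be read as the protocol stating otherwise. The IRB sentence and the capture window carry no such clause.
3. **Other provisions do not close the gap for non-serious events.** Section 6.0 lists imaging duration and operative time as data items, so exposure is measured. It lists no adverse event item, although the list is open. It also plans a symptom contact within 30 days, without saying how the answers are recorded.

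One calculation shows what the rule does to interpretation without assuming an event rate. With zero events in n patients and complete capture, the one-sided 95% upper limit on the true rate is 1 − 0.05^(1/n):

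- n = 5: 1 − 0.05^(1/5) = 0.451
- n = 20: 1 − 0.05^(1/20) = 0.139

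The 13.9% limit holds only for events that the rules let in. A clean record under Sections 9.0 and 12.0 would say nothing comparable about shared-cause events. It also shows that 20 patients are few even with full capture.

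**The case against.** Separating standard-of-care surgical events from research events is deliberate and reasonable. The case against a strong reading is good, and much of it stands.

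A reader might infer that these events have *no route at all* into the safety data. The documents do not support that. The IRB duty in Section 11.0 is unqualified, SAEs are to be captured for 30 days, and the UADE definition reaches effects associated with the device, not only those caused by it.

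A reader might infer that a sedation event would necessarily be classed as surgical. That is not shown either. Section 7.0 attributes the extra minutes to the imaging procedure, Section 9.0 captures events related to HRME imaging rather than to the probe alone, and its exclusion concerns the standard-of-care cone. An event due to the added time can be read as inside the capture rule. For such an event the *definitely* threshold may be the larger barrier.

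A reader might infer that the number recorded would be zero whatever the true rate, or put a count on the events missed. Zero assumes that every such event is classed as surgical and that every other route fails. A count needs an event rate, and the documents give none; Section 7.0 calls the sedation risk a rare possibility.

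Nor would full capture let this study detect an excess of operative complications: it is single-arm, with 20 patients and no stated background rate. Section 10.0 also does not confine the cohort evaluations to case report form entries.

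What these arguments leave untouched is the wording. The exclusions reach partly surgical events, no rule covers mixed attribution, and Section 11.0 says something different about serious events.

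**Conclusion.** The point holds in a limited form. For non-serious events, Sections 9.0 and 12.0 as written can leave shared-cause events out of the protocol data and the case report form, and the handling of an event due to added sedation time is undefined. For serious events, the exclusions contradict Section 11.0 and cloud the UADE route in Section 12.0; the contradiction is unresolved, but a route exists.

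The reach is the whole study: all 20 patients have imaging and cone in one session, with about 10 added minutes by the protocol's own estimate, and every cohort evaluation is affected. The size in events cannot be stated. The conclusion rests on a literal reading of *related to* and on the absence of any stated precedence between the capture rule and the exclusions. If the site already records mixed cases under an unwritten convention, the practical loss is smaller, but the text should still say so. The change should be made: it is cheap and bears directly on safety ascertainment.

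**What to change.** Replace the exclusion sentences in Sections 9.0 and 12.0 with one rule, stated once and cross-referenced:

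- Leave an event out of the protocol data only when it is judged solely due to the standard-of-care cone and its usual anaesthesia, and unrelated to proflavine, HRME imaging or the added operating-room time.
- Record events whose attribution is mixed or uncertain, with the attribution assigned.
- State that the exclusion does not limit SAE reporting under Section 11.0 or UADE reporting under Section 12.0.

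The *definitely* wording in Section 9.0 must be brought into line, since it would otherwise defeat the second item. There is no need to record every anaesthetic event whatever its cause; events due only to the cone's usual anaesthetic can stay out.

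The cost is a text amendment to two sections and a few more recorded events in 20 patients, some of which will prove to be ordinary post-cone events. Sample size, procedures and the Section 10.0 analysis do not change.

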## **Device failure**

Device failures which occur at the time of participant evaluation and which may prevent a participant from receiving therapy on trial will be kept on a log and will be reported as part of the annual report. Device failures at this point are not expected to affect patient safety, as participants may still receive appropriate therapy as determined by their attending physician.

# Appendix A – Flammability

In order to determine the flammability of acriflavine and proflavine topical dyes during the application of endoscopic thermal devices, we performed the following experiments, using both our contrast agents and both types of endoscopic coagulation/cautery devices:

- 1. Acriflavine and Proflavine were separately applied to the mucosal surface of a goat esophagus. Acriflavine 0.05% and 0.5% (1X and 10X the proposed clinical concentrations) was used. Proflavine Hemisulfate at 0.01% and 0.1% (1X and 10X proposed concentrations) was used.
- 2. Immediately, after the dyes were topically applied to the tissue, the two endoscopic coagulation and cautery devices (argon plasma coagulater and monopolar snare-cautery) were applied to the stained tissue at the highest temperature settings used in the esophagus (45-50W).
- 3. To monitor the change in surface temperature as a result of the thermal devices, a handheld infrared temperature meter was used at each site. Each measurement was performed in triplicate and compared to a control site of unstained mucosa (ie. no contrast agent). A summary of the temperature differences at the different sites is shown below in Figure 1 which reflects application of the argon plasma coagulater (APC) and Figure 2 which reflects application of monpolar cautery (MC).

[figure not shown]

Figure 3
